Boosting vaccination uptake using wastewater surveillance: a comparison-control trial

Utilizing wastewater surveillance data in a communications campaign as a driver behind COVID-19 vaccine uptake in New York State

INVESTIGATORS

Principal Investigator

[name] MPH
Syracuse University
[name]
[name]
[contact]
Email: [contact]

Co- investigators

[name]
Center for Environmental Health, New
York State Department of Health
CDC Foundation
Email: [contact]

[name]
Department of Public Health,
Syracuse University
Email: [contact]

[name]
Department of Public Health,
Syracuse University
Email: [contact]

[name]
Center for Environmental Health, New
York State Department of Health
CDC Foundation
Email: [contact]

[name]
Syracuse University
Department of Public Health
Email: [contact]

[name]
Center for Environmental Health, New
York State Department of Health
CDC Foundation
Email: [contact]

[name]
Syracuse University
Department of Public Health
Email: [contact]

INVESTIGATORS	2
PROJECT SUMMARY	4
RATIONALE AND BACKGROUND	5
Objectives	6
TARGET COUNTIES	7
INTERVENTION	7
EVALUATION	7
Study Design	7
Selection of control and treatment counties	7
Outcomes	8
Data to be collected	9
Statistical analyses	9
TIMEFRAME	10
HUMAN SUBJECTS RESEARCH	10
Risks to subjects	10
Adequacy of protection against risks	10
Potential benefits of the proposed research to the subjects and others	10
Data and safety monitoring plan	10
Inclusion of women and minorities	11
Inclusion of children	11
Trial Registration	11
Protocol Accessibility	11
Funding Stream	11
Conflict of Interest Statement	12
Ethical approval	12
APPENDICES	12
Appendix 1 – Letter of Cooperation from New York State Department of Health	12
Appendix 2 – Letter of Cooperation from Local Health Departments	12
REFERENCES	12

PROJECT SUMMARY

Goal	To determine the effect of a communications campaign sharing wastewater surveillance data to influence vaccine uptake in a metropolitan and non-metropolitan environment.
Intervention site	Onondaga and Cayuga counties in New York State
Populations	Individuals of all ages within the selected counties, located in metropolitan and non-metropolitan environments.
Evaluation study design	Comparison-control trial
Primary outcome measures	Proportion of vaccine-eligible individuals in the county that received the COVID-19 vaccine stratified by type of vaccine dosage and age group
Data collection and sampling method	Vaccination data will be aggregated to the county by the State Department of Health and shared with the research team. Wastewater data will be pulled from the wastewater surveillance network.
Statistical and analytic plan	A difference in differences analysis will be used to estimate the effect of the intervention on both the outcomes between intervention and comparison groups following the intervention, while adjusting for potential confounding factors.

RATIONALE AND BACKGROUND

Vaccinations are among the most successful and critical public health interventions. The expanded program for immunizations is responsible for preventing an estimated 4-5 million deaths globally, and capable of preventing an additional 1.5 million deaths with universal global coverage.^{1,2} Despite the enormous protection that vaccines provide to public health, delays and refusals of vaccines (vaccine hesitancy) are on the rise.^{3,4} Vaccine hesitancy leads to lower community-level vaccination rates which threaten resurgences of vaccine-preventable diseases such as polio or measles and increase the severity of seasonal infectious diseases such as influenza.^{5,6} The drivers of vaccine hesitancy are complex, and can vary heavily between different demographic groups. Reasons for vaccine hesitancy tend to fit into three categories: 1) a lack of confidence in effectiveness, safety, system, or policy makers; 2) a perceived lower risk of acquiring a vaccine preventable disease; and 3) a lack of availability, accessibility, and convenience in obtaining a vaccine.^{7,8}

Vaccines are now (as of 2023) the primary prevention intervention for the COVID-19 pandemic in the United States. As of September 2022, 83.4% of New Yorkers statewide have received at least one vaccination dose for COVID-19, and 75.4% have received a completed vaccine series (completed COVID-19 vaccine series and booster).⁹ These percentages vary based on demographics such as race, ethnicity, age, and gender.¹⁰ Rural and urban communities also vary greatly when it comes to COVID-19 vaccination coverage, with rural counties having lower vaccination rates than urban counties across the United States.¹¹ This disparity is present in New York counties as well, with rural counties having lower COVID-19 vaccination uptake (first dose, boosters, completed series) than urban counties.⁹ There are various factors that could contribute to the vaccination coverage disparities between urban and rural counties. Accessibility to healthcare services continues to be a challenge in rural regions, such as a lack of healthcare providers and minimal information on how and where to seek out services.^{12,13}

Given that low vaccination rates present both an individual and community risk, it is critical that public health departments take measures to increase vaccination uptake across New York State. Vaccination communication and education have the potential to change how individuals feel about vaccinations, clarify common and widespread misconceptions, and address vaccine hesitancy in the process.^{8,12} The success of public health campaigns can vary depending on interactions between the message, material, and target communities of the campaign.^{17,18} Therefore, it's important to create an effective communication plan that not only spreads the message of pro-vaccinations, but also caters to the communities that are involved. Vaccine uptake interventions and campaigns often use the health belief model in identifying levers that might motivate individuals to get vaccinated. We hypothesize that infectious disease surveillance data, specifically wastewater surveillance data, can act on the perceived susceptibility of vaccine-hesitant individuals in the health belief model (Figure 1).

The Health Belief Model: Targeted Areas

[figure not shown]

Figure 1: The health belief model as it relates to our hypothesis of using infectious disease surveillance to increase the perceived susceptibility of an individual to COVID-19.

Wastewater surveillance of SARS-CoV-2 has been shown to be a leading indicator of pending surges. Our work in New York State shows that the variability in wastewater data precedes surges in COVID-19 cases by about four weeks (Moran et al. in preparation). This study will examine whether a communications campaign based upon SARS-CoV-2 wastewater surveillance data with a 4-week lead time to surges can increase COVID-19 vaccine uptake.

Objectives

The goal of this trial is to test the effect of a communications campaign based upon wastewater surveillance data on COVID-19 vaccine uptake.

This protocol presents a plan for conducting a strategic communications campaign to identify the impact of sharing public health messaging based upon wastewater surveillance data on COVID-19 vaccination uptake. The specific objectives of this project are to:

1. Assess the impact of a communications campaign on the outcomes of COVID-19 vaccine uptake, including initial dose, complete series, booster dose, and bivalent booster dose by age group, following implementation of the communications campaign in selected metropolitan and non-metropolitan counties.
2. Strengthen the capacity of the New York State Department of Health and local health departments in determining how to apply their resources to disseminate wastewater surveillance data effectively with the general population.

INTERVENTION COUNTIES

The comparison control trial to assess a communications campaign using wastewater surveillance data will be conducted in Onondaga County (metropolitan) and neighboring Cayuga County (non-metropolitan) in New York State. Monroe and Seneca Counties will serve as a comparison to Onondaga and Cayuga Counties, respectively. These counties were selected based on similarities across population density, demographics (age, sex, race, ethnicity), wastewater surveillance population coverage, and vaccination rates.

INTERVENTION

In intervention communities we will deploy a COVID-19 vaccine communications campaign based upon the increasing variability in the amounts of SARS-CoV-2 RNA found in wastewater. (Increasing variability in the amounts of SARS-CoV-2 RNA in wastewater acts as a 4-week leading indicator, Moran et al. in preparation). Through the New York State Wastewater Surveillance Network, wastewater samples are analyzed to determine whether COVID-19 trends are increasing or decreasing in the community. This information is then shared with county health officials to better improve understanding of the underlying COVID-19 transmission risk.

Social media will be used to disseminate wastewater surveillance data and vaccination information to residents in Onondaga and Cayuga Counties. Social media platforms will not only allow for quick and cost-effective exposure, but also will allow for participation and interaction with participants. In addition, local health departments will be engaged to enhance their press releases and public health advisories to their communities.

EVALUATION

Study Design

We will use a difference-in-differences (DiD) method to assess the impact of the communications campaign on vaccine uptake. The DiD method observes the outcomes between a control and intervention group over pre- and post-intervention time periods.

Selection of control and treatment counties

The counties were selected based on the following criteria:

1. Population density: metropolitan vs. non-metropolitan area
2. Demographics (age, sex, race, ethnicity)
3. Wastewater surveillance coverage: population served and sampling frequency
4. COVID-19 vaccination rates

The U.S. Office of Management and Budget defines Monroe and Onondaga as metropolitan counties with an urban core of 50,000 or more people, while Seneca and

Cayuga are defined as non-metropolitan counties an urban core of 10,000-49,999 people or as being outside of metro areas. The metropolitan and non-metropolitan counties also shared similar demographics, wastewater surveillance coverage, COVID-19 vaccination rate.

COVID-19 vaccine coverage across the included counties is presented in Table 1. Table 1 also provides other county-level metrics that might be associated with vaccine uptake including the social vulnerability index, population density, number of corner-store pharmacies that serve as vaccine providers, and average income.

Table 1: County-level metrics with possible association with vaccine uptake.					
		Metropolitan Counties		Non-Metropolitan Counties	
		Monroe	Onondaga	Seneca	Cayuga
COVID-19 vaccine coverage	Primary Series	74.0	74.0	53.9	60.8
	Up to Date	17.3	15.9	11.4	12.0
Social vulnerability index	Socioeconomic Status	0.4426	0.4918	0.4918	0.6066
	Household Characteristic	0.8525	0.7377	0.5738	0.3443
	Racial & Ethnic Minority Status	0.8361	0.7377	0.4754	0.4262
	Housing Type & Transportation	0.4754	0.7541	0.4098	0.7213
Pharmacies	per 10,000 People	1.87	2.21	1.46	2.08
Population	Number	743084	461591	34016	76958
	Density per sq mile	1125.1	590.2	105.81	110.47
Income	Median Household Income (\$)	65,957	65,541	54,865	63,511
Vaccination data as of 11/18/22 from: https://coronavirus.health.ny.gov/vaccination-progress-date					
People with primary series represents the total number of individuals who have completed the recommended initial series of a given COVID-19 vaccine product (e.g., 2 doses of the 2-dose Pfizer or Moderna vaccine; 1 dose of the single dose Johnson & Johnson vaccine).					
People up to date represents the total number of individuals who have completed all COVID-19 vaccinations, including the bivalent booster, as appropriate per age and clinical recommendations (CDC At-A-Glance COVID-19 Vaccination Schedules).					
Social Vulnerability Index from: https://www.atsdr.cdc.gov/placeandhealth/svi/interactive_map.html					
Theme rankings: For each of the four themes, we summed the percentiles for the variables comprising each theme. We ordered the summed percentiles for each theme to determine theme-specific percentile rankings.					
Population 2020 Estimates					

Outcomes

The communications campaign will be evaluated using the change in vaccination status of residents of the treatment and control counties. Change in vaccination status will be

broken down by type of vaccine dose (e.g., initial series v. booster dose) and age because vaccine eligibility varies by age group (Table 2).¹⁹

Table 2: Proposed age and vaccine dose breakdown for vaccination outcomes.		
Age group	Primary Series	Up to Date with bivalent booster
18+	85.2	12.3
12-17	73.1	4.2
5-11	39.6	1.9
Under 5	6.2	--

Notes: People with primary series represents the total number of individuals who have completed the recommended series of a given COVID-19 vaccine product (e.g., 2 doses of the 2-dose Pfizer or Moderna vaccine; 1 dose of the single dose Johnson & Johnson vaccine). People up to date represents the total number of individuals who have followed and completed the all COVID-19 vaccinations, including the bivalent booster, as appropriate per age and clinical recommendations ([CDC At-A-Glance COVID-19 Vaccination Schedules](#)). Vaccination progress tracking in New York was updated 11/30/22 to reflect the most current ACIP recommendations.

Data from <https://coronavirus.health.ny.gov/demographic-vaccination-data>

The change in vaccination coverage among residents of the counties in the study will be measured as the percent of the population that received a vaccine dose. Outcomes will also be compared between demographic groups including race and ethnicity because of differences in vaccination rates that have been already observed.²⁰

Data to be collected

All data used in this study is routinely gathered and disseminated by the New York State Department of Health. No individual human data will be collected as part of the study.

Statistical analyses

We will use a difference-in-differences (DiD) method to evaluate the effectiveness of the communications campaign using the following equation:

$$DiD = E(Y_1^T - Y_0^T | T_1 = 1) - E(Y_1^C - Y_0^C | T_1 = 0)$$

The DiD is calculated from the differences between the treatment group ($T_1 = 1$) and the control group ($T_1 = 0$) from their initial condition at $t = 0$ or time zero. The change in each group is compared to determine if the intervention resulted in different outcome in the treatment group. In our study, the outcome is the percent of the county populations that received COVID-19 vaccines during the study period and whether the treatment counties had greater vaccination rates by the end of the study than the control counties. We will determine the statistical significance for DiD using a regression framework where the mean vaccination rate (Y) is predicted by whether the county received the treatment (the communications campaign) or not. The mean will be determined for the total vaccination rate as well as each of the age categories identified in Table 2.

TIMEFRAME

Table 3: Time frame for proposed activities

Project Years:	2022				2023			
	Q1	Q2	Q3	Q4	Q1	Q2	Q3	Q4
Finalization of Communication Campaign Intervention								
Baseline Measures								
Communications Campaign								
Endline Measures								
Data Analysis								
Dissemination of results								

HUMAN SUBJECTS RESEARCH

Risks to subjects

No reasonably foreseeable risks, discomforts, hazards, or inconveniences are anticipated in relation to the communications campaign. All data used will be non-human data (aggregated County vaccine coverage for example).

Adequacy of protection against risks

We are requesting a waiver of informed consent for this project. Since we are using existing clinical testing and wastewater surveillance data, this study could not be practically carried out without a waiver of informed consent. A letter of cooperation signed by the local health departments overlooking the selected sewersheds/counties involved in this research will be provided.

Potential benefits of the proposed research to the subjects and others

Populations in the selected counties may expect increased vaccination rates, leading to herd immunity against SARS-CoV-2. Additionally, increased education and knowledge on the correlation between communications and vaccination rates will be made available.

Data and safety monitoring plan

We are continuing to collect wastewater surveillance data from the selected sewersheds for analysis and updating the New York State Wastewater Surveillance Network platform. At no point will any individual within the scope of surveillance be identified or exposed to any potential harm. Data monitoring to evaluate risks or harm to participants

will not be needed for this project. All data used in this study are de-identified and aggregated to county level.

Inclusion of women and minorities

We anticipate that half of the research subjects will be women, given the demographic composition of the population. Our study will be conducted in two non-metropolitan counties (Seneca and Cayuga) and two metropolitan counties (Onondaga and Monroe), where the racial and ethnic profile of the communities is homogenous. We do not expect to find significant race/ethnicity differences in the intervention effect.

Inclusion of children

Children are not a major focus of this research, but we do expect children between the ages of 1 month and 5 years of age to fall within the scope of the areas being considered for this study.

Trial Registration

To ensure external review of the protocol and to allow easy access for entry into subsequent systematic reviews, this trial will be registered with ClinicalTrials.gov prior to distribution of any communications materials. This is in accordance with the WHO statement that “The registration of all interventional trials is a scientific, ethical and moral responsibility” (<http://www.who.int/ictrp/en/>).

Protocol Accessibility

The complete protocol will be submitted to a peer-reviewed journal ahead of intervention delivery in the study site. This will prevent the likelihood of undeclared post-hoc changes to the protocol following IRB submission and of selective outcome reporting when the trial results are published. Additionally, this will provide peers and relevant partners working in the arena of wastewater surveillance and public health communications, advanced warning of a trial being planned for and provide opportunity not to duplicate similar intervention studies where the outcomes of this trial may hold external validity for their given wastewater-based epidemiology setting.

Funding Stream

The evaluation will be funded through the CDC Epidemiology and Laboratory Capacity program via funding awarded to NYSDOH. The funders will have a significant role in the study design. However, the funders will have no role in the data collection and analysis, decision to publish or preparation of the manuscript for protocol publication and trial outcome research article.

Conflict of Interest Statement

The Principal and Co-investigators along with other personnel involved with the implementation of this trial are not affiliated or employed by the funding organization. Additionally, none of the associated individuals are employed, affiliated or hold stocks or shares in the organizations, that through a competitive bidding tender process, will provide wastewater analysis, or vaccination data related to the primary outcomes in the trial.

Ethical approval

The trial will be submitted for ethical approval to the IRB at Syracuse University (USA) and the New York State Department of Health.

APPENDICES

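### The significance test rests on two treated and two comparison counties with no stated unit or error structure; on county changes it has 2 residual df at most, and no room for several county covariates

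*Combined protocol and SAP*

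**What the plan says.** The Intervention Counties section assigns the campaign to Onondaga and Cayuga and fixes the comparators: "Monroe and Seneca Counties will serve as a comparison to Onondaga and Cayuga Counties, respectively". The Project Summary says "Vaccination data will be aggregated to the county by the State Department of Health and shared with the research team", and the Data and safety monitoring plan confirms it: "All data used in this study are de-identified and aggregated to county level".

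The Outcomes section makes change the quantity of interest: "The communications campaign will be evaluated using the change in vaccination status of residents of the treatment and control counties". The equation in the Statistical analyses section likewise takes the change in the treated group minus the change in the control group. That section then says "We will determine the statistical significance for DiD using a regression framework", in which "the mean vaccination rate (Y) is predicted by whether the county received the treatment". It repeats the calculation for the total and for each age category in Table 2. It gives no number of rows or time points, no county, pair or period terms, no variance estimator, no weights and no alpha. The plan has no sample size or power section.

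The statistical row of the Project Summary adds that the effect will be estimated "while adjusting for potential confounding factors". No factor is named there, and no covariate appears in the Statistical analyses section. Table 1 lists county metrics that may bear on uptake but does not call them model covariates.

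**The concern.** A treatment given to whole counties is replicated only as often as there are counties. With two per arm, the choice of error term largely decides the result, and the plan leaves that choice to the analyst. If the county is the unit, the critical values are very large and a null result may say little about the campaign. If residents, weekly dates or age strata are treated as independent, county-to-county variation drops out of the error and chance differences between counties can appear highly significant. This is the plan's only inferential step and it serves the primary outcome. The adjustment promised in the summary also needs degrees of freedom that a four-county model does not have.

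**Working it through.** The plan states no df, power or alpha, so there is no figure of its own to reproduce. Two-sided 0.05 and 80% power are assumed below.

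**Inputs.** Two treated and two comparison counties, in two pairs (Intervention Counties). County aggregates (Project Summary; Data and safety monitoring plan). Table 1 populations: Onondaga 461,591, Cayuga 76,958, Monroe 743,084, Seneca 34,016.

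**1. Residual df = rows − parameters, with the county change as outcome.**
- Intercept + treatment: 4 − 2 = 2. County and period effects on eight county-period values give the same: 8 − 6 = 2.
- Adding the pair term, or one Table 1 metric: 4 − 3 = 1.
- Two metrics, or the pair term plus one metric: 4 − 4 = 0, so there is no standard error and no test. Design-matrix ranks for seven Table 1 metrics (four vulnerability themes, pharmacies, density, income) gave 0 df for all 21 two-metric combinations, and for the pair term with each metric.

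Two-sided 5% critical t: 4.30 at 2 df and 12.71 at 1 df, against 1.96 for the normal.

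**2. Power in SD units.** With two against two, SE = SD × √(1/2 + 1/2) = SD, where SD is the between-county SD of change. For the mean of two pair differences, SE = √(2 × SD²/2) = SD, where SD is the within-pair county SD. From the noncentral t:

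| df | 1 SD | 2 SD | 3 SD | effect for 80% power |
|---|---|---|---|---|
| 2 | 10% | 22% | 39% | 5.65 SD |
| 1 | 7% | 13% | 19% | 16.3 SD |

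**3. Percentage points.** Table 1 shows levels at one date, so no SD of change can be taken from it. Over an assumed range:

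| assumed SD (pp) | effect for 80% power, 2 df (5.65 × SD) | same, 1 df (16.33 × SD) | power for 1 pp, 2 df |
|---|---|---|---|
| 0.1 | 0.6 pp | 1.6 pp | 99% |
| 0.25 | 1.4 pp | 4.1 pp | 56% |
| 0.5 | 2.8 pp | 8.2 pp | 22% |
| 1.0 | 5.7 pp | 16.3 pp | 10% |

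**4. What a resident-level error term would do.** Arm totals are 461,591 + 76,958 = 538,549 and 743,084 + 34,016 = 777,100. With an assumed 3% newly vaccinated, SE = √[0.03 × 0.97 × (1/538,549 + 1/777,100)] = 0.030 pp, so a difference of 1.96 × 0.030 = 0.059 pp would be significant. The population shares within arms are 0.857 and 0.143, and 0.956 and 0.044; their squares sum to 1.67. The true variance of the difference is therefore 1.67 × SD² + 0.030². For an SD of 0.1 pp its root is 0.133, and 0.059/0.133 = 0.45 gives a true type I error of about 66%. For an SD of 1.0 pp it is about 96%.

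**5. The optional placebo test, by simulation.** Each county's change is compared with the mean of the others in its class (metropolitan or non-metropolitan), and the average for the two treated counties is ranked among all metropolitan/non-metropolitan pairs. With m = 4, 9 or 19 untreated counties per class (assumed), independent counties and equal SDs, size was 3.9%, 5.0% and 4.8%, and power at 2 SDs was 51%, 70% and 77%. If the two treated counties' changes correlate at an assumed 0.5 to 0.8, size rises to about 7% to 14%. If their SD is 1.5 times that of the others, size rises to about 9% to 17%.

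**The case against.** **The df count depends on the reading.** This stands in part. The plan does not fix the number of rows. A pooled regression on eight county-period levels has 4 nominal df (critical t 2.78), and weekly data would show more (20 with four weeks per period). But such models either ignore that the same four counties are measured repeatedly or count dates as replicates. The change-score reading is the one that fits the plan's equation and its Outcomes section.

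**The covariate promise is general.** This stands. The summary names no factor and does not say that adjustment means regression terms. Differencing already removes fixed additive county effects, the counties were chosen for similarity, and results are split by age. A reader might infer that no adjustment of any kind is possible; the documents do not support that. What cannot be done is to fit several county covariates in the four-county change model.

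**Low power is not shown.** This stands. A reader might infer that the trial is underpowered. Without an SD of change or a target effect, the documents support only that power is unknown. The section's wording also allows a one-sided test, which at 2 df lowers the requirement from 5.65 to 3.98 SDs.

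**A 2-df t-test is valid.** This stands under independent, equal-variance, normal changes. Barring every four-county p-value would be partly a preference.

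**Separate settings.** Objective 1 looks at uptake "following implementation of the communications campaign in selected metropolitan and non-metropolitan counties". A reader might infer that a separate test in each setting is promised. None is. Each setting is one county against one, with no county-level error estimate, so results by setting can only be descriptive.

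**Conclusion.** The point holds for a county-level analysis of changes. The plan bases significance on four units without naming the unit or the error term. That analysis has 2 residual df, or 1 with the pairs, and none once two county covariates, or the pairing plus one, are included. The SD multiples rest on an assumed two-sided 0.05 and on independent, normal changes of equal variance. The resident-level error rates rest on the assumed uptake and SDs. The df counts rest only on the number of counties and the model terms. It should be settled before analysis, because the unspecified choice lies between a test that may be uninformative and one that is falsely precise.

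**What to change.** 1. In the Statistical analyses section, name the county as the unit and the baseline-to-endline change as the outcome. State that residents, dates and age strata will not be counted as independent replicates.
2. Report the matched-pair DiD, overall and for each pair, as the main, descriptive estimate. If a four-county test is kept, base it on county changes with the t reference at 2 df (1 df if paired), report the interval, and state that a null result is not evidence of no effect.
3. Reconcile the Project Summary with the Statistical analyses section by removing multi-covariate adjustment from the four-county model.
4. Optionally, for one named outcome, pre-specify the class-based placebo-rank test as a supportive analysis. Attach its p-value and interval to its own estimate, not to the matched-pair DiD. State the p-value floors from the actual class sizes, which the documents do not give: 1/(m + 1) for one county (m = 19 gives 0.05) and 1/[(m1 + 1)(m2 + 1)] for the average (4 and 4 give 1/25 = 0.04). Confirm first that comparable data exist for the other counties.

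Items 1 to 3 cost only wording, and reported precision will look less favourable. Item 4 needs a wider pull of routine state data but no new sites. It assumes exchangeability within class, equal variances and no shared shock between the treated counties, which are neighbours; the size inflation shown above is the price if these fail. Any gain over the four-county test is not like for like, because it uses more counties and they are not matched.

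### The matched county pairs are dropped from the regression and the county weighting is unstated: pooling residents could bias the DiD, and different weightings estimate different effects

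*Combined protocol and SAP*

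**What the plan says.** The INTERVENTION COUNTIES section says that the trial "will be conducted in Onondaga County (metropolitan) and neighboring Cayuga County (non-metropolitan) in New York State" and that "Monroe and Seneca Counties will serve as a comparison to Onondaga and Cayuga Counties, respectively". These are two matched pairs, one metropolitan and one non-metropolitan, and the Project Summary states the goal for both kinds of setting.

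The Statistical analyses section gives one DiD equation: mean change from time zero in the treatment group minus mean change in the control group. It then describes the outcome as the percent of county populations vaccinated during the study and "whether the treatment counties had greater vaccination rates by the end of the study than the control counties". Significance is to come from a regression in which "the mean vaccination rate (Y) is predicted by whether the county received the treatment (the communications campaign) or not". The next sentence adds: "The mean will be determined for the total vaccination rate as well as each of the age categories identified in Table 2".

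The section names no pair or metropolitan term, no period or treatment-by-period term, and no rule for weighting the counties. The Project Summary promises adjustment for confounders, but it names none, and the analysis section does not carry the promise into the model.

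**The concern.** The pairing was chosen so that each treated county is judged against a control of the same type. An analysis with a single treated/untreated term on a mean rate keeps that protection only if both arms end up with the same metropolitan/non-metropolitan mix. Whether they do depends on how the two counties in each arm are averaged, and the plan does not say.

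Two things are at stake. If residents are pooled, the arms have different mixes, and any difference in uptake gain between metropolitan and non-metropolitan counties enters the DiD as if it were a campaign effect. If counties count equally, that bias disappears, but the result is a different average of the two county effects. The stated goal covers both settings, and a single pooled coefficient reports neither.

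**Working it through.** The plan states no pooled estimate, alpha or sample size, so there is no figure of its own to reproduce. All inputs come from Table 1, in the order Monroe, Onondaga, Seneca, Cayuga:
- population: "Number 743084 461591 34016 76958"
- primary-series coverage, %: "Primary Series 74.0 74.0 53.9 60.8"
- up-to-date coverage, %: "Up to Date 17.3 15.9 11.4 12.0"

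**1. Metropolitan share of each arm if residents are pooled**
- Treated: 461,591 / (461,591 + 76,958) = 461,591 / 538,549 = 85.7%
- Control: 743,084 / (743,084 + 34,016) = 743,084 / 777,100 = 95.6%
- Difference, treated minus control: 0.8571 - 0.9562 = -0.099

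**2. DiD when the campaign does nothing.** Let metropolitan counties gain *a* points and non-metropolitan counties gain *b* points, the same in both arms.
- Population weights: DiD = [0.8571a + 0.1429b] - [0.9562a + 0.0438b] = -0.099 × (a - b)
- Assumed a - b = 2: -0.20 point. Assumed a - b = 5: -0.50 point.
- Equal weights: DiD = (a + b)/2 - (a + b)/2 = 0, with or without a pair term

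**3. DiD when the campaign effect differs by county.** Assume an effect of 0 in Onondaga and +2 in Cayuga, with equal underlying gains.
- Equal weights: (0 + 2)/2 = +1.00
- Population weights: 0.8571 × 0 + 0.1429 × 2 = +0.29

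**4. Baseline gap, treated minus control, as an illustration of sensitivity only**
- Primary series, equal weights: (74.0 + 60.8)/2 - (74.0 + 53.9)/2 = 67.40 - 63.95 = +3.45
- Primary series, population weights: 72.11 - 73.12 = -1.01
- Up to date, equal weights: 13.95 - 14.35 = -0.40
- Up to date, population weights: 15.34 - 17.04 = -1.70

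For primary series the within-pair gaps are 74.0 - 74.0 = 0.0 and 60.8 - 53.9 = +6.9. Any common weighting of the pairs must lie between 0 and +6.9, so the -1.01 comes from the unequal mix and not from either pair.

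**5. What a pair-by-period regression would do.** Least squares weights each pair by (treated weight × control weight) / (sum of the two).
- Unweighted rows: 50/50
- Population-weighted rows: 461,591 × 743,084 / 1,204,675 = 284,725 for the metropolitan pair, and 76,958 × 34,016 / 110,974 = 23,589 for the non-metropolitan pair, that is 92.3/7.7
- Treated-county population: 85.7/14.3

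Under the effects assumed in step 3, these give +1.00, +0.15 and +0.29.

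**6. Degrees of freedom**, taking one row per county at baseline and one at endline: 4 × 2 = 8 rows.
- County effects (4), period (1) and treatment-by-period (1) use 6, leaving 2.
- Replacing the period term by one for each pair (2) uses 7, leaving 1.
- The two-sided 5% critical t rises from 4.30 to 12.71 (alpha is assumed; the plan gives none).

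**The case against.** The strongest reply is that the plan never proposes population weights. Data are aggregated to county and the predictor is defined for the county, so the natural row is a county. Each arm has one metropolitan and one non-metropolitan county, so equal weighting is balanced by construction and adding a pair term leaves the point estimate unchanged. This stands, and it confines the bias to the pooled-resident analysis. It does not settle which analysis is planned, because the section speaks both of a mean rate and of the percent of county populations vaccinated.

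Three stronger readings are tempting and are not supported.
- A reader might infer from the baseline gap moving from +3.45 to -1.01 that the effect estimate would flip too. A fixed gap cancels in the DiD equation, which is written in changes. It would enter the result only if the regression were run on end-of-study levels, as its wording allows. The flip also occurs for primary series only; the up-to-date gap keeps its sign.
- A reader might infer that unequal trends are likely because the background reports lower rural coverage. That is a statement about levels. The documents give no difference in gain over the study period, so the 2 and 5 points above are assumptions.
- A reader might infer that weighting could reverse the sign of the campaign effect. With equal underlying gains, that needs effects of opposite sign in the two counties: assumed effects of -1 in Onondaga and +2 in Cayuga give +0.50 with equal weights and -0.57 with population weights. Nothing in the documents points to such a pattern.

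The confounder adjustment promised in the Project Summary may have been meant to cover metropolitan status, but it does not say so.

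**Conclusion.** The point holds in a limited form. The design is paired and the stated regression is not, and the county weighting is open. Under pooling of residents, the error is -0.099 point per point of metropolitan minus non-metropolitan difference in gain. That rests on Table 1 total populations and on the same gains in both arms apart from the campaign. Under equal county weights there is no such error, but the estimand can differ materially from the population-weighted one whenever the two treated counties respond differently. The documents do not show that the eventual estimate will be biased. They do leave open a choice on which it depends, and the paired design offers a better analysis at no cost in data.

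**What to change.** In Statistical analyses, replace the single treatment term with the following:
- For each outcome and age group, calculate the DiD in change from baseline within Onondaga-Monroe and within Cayuga-Seneca, and report both. This also answers the metropolitan and non-metropolitan parts of the goal.
- Combine the two as an explicit weighted average, with one prespecified set of weights applied to both arms. One option is the treated-county eligible population, about 85.7/14.3 if Table 1 total populations stand in for eligible numbers, which the documents do not give by county.
- Reword the sentence about end-of-study rates so that the comparison is of change from baseline.

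A pair-by-period regression should not be treated as equivalent, because it sets its own pair weights (50/50 unweighted, about 92.3/7.7 population-weighted). If one is used for testing, its implied weights should be stated.

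The change is to wording only and needs no new data. The real cost is in inference: a pair-by-period model has 1 residual degree of freedom instead of 2, already a very small number. The pair results should therefore be presented mainly as estimates, and the plan should describe formal inference as very weak.
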